Pharmacokinetics of *Centella asiatica* in the Elderly

NCT03929250

STUDY PROTOCOL INCLUDING STATISTICAL ANALYSIS PLAN

Document Version Date: February 28, 2024

Study Title: A pharmacokinetic study of *Centella asiatica* in the elderly

Principal Investigator: [name]

IRB#: 17697

Date: Feb 28 2024

Protocol v4.0

Title: A pharmacokinetic study of *Centella asiatica* in the elderly

A. OBJECTIVES

A.1. Purpose

The purpose of this pilot study is to measure the oral bioavailability and pharmacokinetics of known bioactive compounds from a standardized *Centella asiatica* water extract product (CAP) in cognitively healthy elders. Compound levels will be measured in human plasma and urine over 12 hours after acute oral administration of two doses of the botanical extract product. The dose giving maximum plasma levels (C_{max}) closest to those observed in our mouse studies, as well as the rate of clearance ($t_{1/2}$) of the known compounds, will be identified. These data will be used to inform decisions on the dosage and dosing frequency for future phase 1 and phase 2 clinical trials.

A.2. Primary goal

To determine the oral bioavailability and pharmacokinetics of known compounds from two single administrations of a *Centella asiatica* product in non-demented elders.

A.3. Endpoints

- The primary endpoints for this study are the maximum concentration (C_{max}), the area under the curve (AUC), and the time of maximum concentration (t_{max}) of known compounds from *Centella asiatica* (triterpenes and caffeoylquinic acids and their metabolites) in human plasma.
- A secondary endpoint is the half-life ($t_{1/2}$) of the known bioactive compounds and their metabolites to help determine dosage intervals.
- Additional secondary endpoints include temporal changes in ferric reducing ability of plasma (FRAP) as an indicator of antioxidant potential over time, tolerability and detection of acute adverse events through monitoring by participant interviews, biometrics, vital signs and questionnaires.

B. SPECIFIC AIMS

Aim 1: To assess the bioavailability and rate of clearance of *Centella asiatica* derived compounds in cognitively healthy elders through a pharmacokinetic study.

- **Hypothesis:** We hypothesize that the triterpene and caffeoylquinic acid components from *Centella asiatica* will be bioavailable, and a dose giving similar plasma levels to those associated with cognitive effects in mice can be achieved.

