Centella asiatica water extract is comprised of 0.94-2.41% triterpenes and 0.01-0.46% caffeoylquinic acids.³¹ The abundant triterpenes asiaticoside and madecassoside are known to metabolize to the neuroactive metabolites asiatic acid and madecassic acid *in vivo*.⁹⁹ Similarly, the caffeoylquinic acids metabolize to caffeic acid, ferulic acid, isoferulic acid, and their dihydroderivatives.^{100,101} Working with OHSUs' Bioanalytical Shared Resource/Pharmacokinetic Core (BSR/PKC) we have developed a sensitive methodology using HPLC-MS/MS to separate and analyze the triterpenes, caffeoylquinic acids, and their further metabolites within a human plasma matrix. Linear calibration curves have been obtained for each of these analytes (25–2000 ng/mL for asiatic acid, 5–2000 ng/mL for madecassic acid, and 5–100 ng/mL for several caffeoylquinic acids and their metabolites).

Previous pharmacokinetic literature in rodents and dogs has reported maximum concentrations of the polar caffeoylquinic acid compounds within one hour of ingestion^{101,102} and the less polar triterpenes at 4-5 hours.¹⁰³ We have performed a pharmacokinetic study in wild-type mice on a low phytochemical diet to identify the C_{max} and time to reach C_{max} (t_{max}) of *Centella*'s known bioactive compounds using the standardized water extract. We were able to detect the bioactive caffeoylquinic acids and their metabolites in plasma following oral administration of the extract using reversed phase HPLC-MS/MS (Figure 2). Maximum plasma concentrations (C_{max}) of CQAs and metabolites (15 – 2350 ng/ml) primarily occurred within 45 minutes of oral administration (Figure 2) and there were no observable adverse events after extract administration. These results demonstrate *Centella asiatica* water extract is orally bioavailable and well-tolerated in mice warranting further evaluation in humans. They also confirm the proposed metabolism of caffeoylquinic acids from *Centella asiatica* water extract into their respective metabolites. To assess for changes in the bioavailability of the standardized manufactured product to be used for this study (CAP), we will perform another mouse bioavailability study.

Table 1. Pharmacokinetic parameters of caffeoylquinic acids and metabolites in mouse plasma after single oral administration of *Centella asiatica* water extract.

Analyte	C_{max} (ng/mL)	t_{max} (min)
---------	-------------------	-----------------

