Study Title: A pharmacokinetic study of *Centella asiatica* in the elderly

Principal Investigator: [name]

IRB#: 17697

Date: Feb 28 2024

Protocol v4.0

[figure not shown]
[figure not shown]
[figure not shown]
[figure not shown]

Figure 2. Pharmacokinetic profile of monocaffeoylquinic acids, dicaffeoylquinic acids and metabolites caffeic acid and ferulic acid in wild-type female mice. Six-month-old female mice (n=39) were administered *Centella asiatica* water extract (200 mg/kg) via oral gavage. Four mice were euthanized per time point and blood collected via cardiac puncture for analysis with HPLC-MS/MS.

F. RESEARCH DESIGN AND METHODS

F.1. Study design

This is a phase 1 pilot clinical study using a blinded randomized crossover design.

Randomization will use an arm equivalence design to promote equal numbers of participants for each order schema. We will dispense a single administration of a *Centella asiatica* water extract

Study Title: A pharmacokinetic study of *Centella asiatica* in the elderly

Principal Investigator: [name]

IRB#: 17697

Date: Feb 28 2024

Protocol v4.0

product to the research participants at two doses (2g and 4g) on two separate occasions two to four weeks apart (Figure 3). Participants will be required to adhere to a “low phytochemical diet” known as a “low plant diet” designed by the Oregon Clinical and Translational Research Institute’s (OCTRI) Bionutrition Department for 48 hours immediately preceding each study visit and for the duration of each study visit (Section I.4.). We will provide participants a handout at screening outlining the diet with meal examples. Serial blood samples (2 teaspoons; 10 mL/sample) will be obtained through a peripheral intravenous catheter, once prior to *Centella asiatica* consumption and then over a 12-hour post-administration period (15, 30, 45, 60, 90, 120, 180, 240, 360, 480, 600, and 720 min). Participants will also perform a 12-hour urine collection at each study visit to assess for excretion of *Centella asiatica* metabolites. Adverse events and tolerability will be assessed with questionnaires in-person at each study visit, by phone 24 hours after each study visit, and one week following study completion (Figure 3).

F.2. Study Population

F.2.1. Number of participants

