Each analyte of interest from *Centella asiatica* will be identified by its retention time and characteristic mass spectral fragmentation pattern using selected reaction monitoring (MS/MS). The peak area ratio to the appropriate internal standard will be identified and evaluated against the standard calibration curve of each analyte. Each analyte's concentration will be used to generate a concentration-time curve for pharmacokinetic profiling. Pharmacokinetic profiling will use non-compartmental analysis to calculate common pharmacokinetic parameters such as peak concentration (C_{max}), the time at peak concentration (t_{max}) and the total 12-hour bioavailability represented by the total area under the curve (AUC_{0-12}). These will be compared to our mouse data in order to assess appropriateness of dosing level. Other calculable non-compartmental analysis metrics will also be determined, such as the elimination half-life ($t_{1/2}$) calculated from the profile tails and the mean residency time of the compounds in plasma. Descriptive assessment will be done at each of the doses to give basic pharmacokinetic summarization of the various *Centella asiatica* compounds and total antioxidant compounds measured by ferric reducing ability of plasma. Dose dependence of the study outcomes will be determined by evaluation of the within-subject differences in study outcomes between the different doses. For all continuous variables, dose effects will be evaluated both naively using paired t-tests and with ordinary least-squares regression with correction for commonly cited confounders including but not limited to baseline age and gender. Assumptions of normality will be confirmed using outcome density distributions alongside utility from formal tests, such as the Anderson-Shapiro. In instances of normality violation, statistical transformation such as natural logs and square roots will be considered, as will non-parametric equivalent tests such as the paired Wilcoxon rank-sum test. Standard diagnostics will be very conservative given the limited number of available participants but the effect of removing clearly obvious outliers will be evaluated. Although all *Centella asiatica* compounds of interest and pharmacokinetic parameters are defined *a priori*, multiple comparison correction to p-values will be applied as necessary, with final two-tail significance defined at $p<0.05$.

L.2. Sample size

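### L.1 sets no analysis scale in advance for Cmax and AUC, misnames the paired fallback test and gives tmax no method of its own, and L.2's within-gender claim is not delivered at n=4

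*Combined protocol and SAP*

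**What the plan says.** Section A.3 lists three primary plasma endpoints: "The primary endpoints for this study are the maximum concentration", the AUC and tmax. Section L.1 then sets out the dose comparison.

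- The quantity tested is paired: "Dose dependence of the study outcomes will be determined by evaluation of the within-subject differences in study outcomes between the different doses".
- The default is "For all continuous variables, dose effects will be evaluated both naively using paired t-tests", together with ordinary least-squares regression adjusted for age, gender and possibly other covariates.
- The check is "Assumptions of normality will be confirmed using outcome density distributions alongside utility from formal tests, such as the Anderson-Shapiro".
- The fallback is "In instances of normality violation, statistical transformation such as natural logs and square roots will be considered, as will non-parametric equivalent tests", and the example of a non-parametric test is given as "such as the paired Wilcoxon rank-sum test".

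Section L.2 sizes the study on a published single-dose study of a triterpene fraction in 12 males, with d=1.57 for Cmax and d=1.42 for AUC. It assumes that exposure shifts in proportion to dose. It concludes that six participants suffice for Cmax and seven for AUC, and that four men and four women will also allow a dose response to be shown in each gender separately. Section F.2.1 accepts a fall to six completers.

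**The concern.** Four things are left open or wrong.

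1. **Scale.** Nothing fixes raw or log for Cmax and AUC. If the normality check raises no flag, skewed exposures are reported as a raw mean difference, although L.2 reasons in ratios. If it does, log, square root and a rank test are all available, with no order, and the choice is made with the data in hand.
2. **Object and form of the check.** A paired t-test needs roughly normal within-subject differences. L.1 speaks of outcome distributions and does not state that the differences are checked. No test is called Anderson-Shapiro; the name appears to merge Anderson-Darling with Shapiro-Wilk.
3. **Name of the rank test.** The rank-sum test is for independent samples. The paired test is the signed-rank.
4. **tmax.** It can take only the 12 scheduled post-dose times, spaced 15 minutes apart at first and 120 minutes apart after four hours. Ties and uneven steps are built in, yet it goes to a comparison of means.

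At stake is whether the primary dose comparison is fully prespecified, and whether L.2's within-gender promise can be met by any of the named tests.

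**Working it through.** **Reproducing L.2.** Two-sided paired t-test, alpha 0.05, df = n−1, noncentrality d√n.

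- Cmax, d=1.57: power 0.747 at n=5 and 0.863 at n=6, so n=6 is the minimum.
- AUC, d=1.42: power 0.792 at n=6 and 0.876 at n=7, so n=7 is the minimum.

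Both stated sizes reproduce. The d values are close to mean difference over pooled SD:

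- Cmax: (1.36−0.70)/√((0.38²+0.45²)/2) = 1.585
- AUC: (9.39−4.16)/√((3.81²+3.53²)/2) = 1.424

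Using them as paired effect sizes implies a within-subject correlation of about 0.5. That value is used below; the documents do not state it.

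**Within gender, n=4.**

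- Paired t-test, Cmax: noncentrality 1.57×2 = 3.14, power 57%.
- Paired t-test, AUC: noncentrality 1.42×2 = 2.84, power 49%.
- Signed-rank: the smallest two-sided p is 2/2⁴ = 0.125, so it can never reach 0.05. At n=6 and n=8 the floors are 0.031 and 0.0078.
- A literal rank-sum, 4 against 4, could reach 2/70 = 0.029, but it ignores the pairing. Run on paired data at n=8 with correlation 0.5, its null rejection rate falls to about 1%.

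**Is skew plausible?** A normal distribution with the low-dose AUC figures (4.16, SD 3.81) puts Φ(−4.16/3.81) = 14% of values below zero. For low-dose Cmax (0.70, SD 0.38) it is 3%. This concerns the values at one dose, not the differences.

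**How often does the open choice matter?** Simulation used L.2's means and SDs and correlation 0.5, with lognormal or gamma shape assumed. The check is taken as Shapiro-Wilk at 5%. If it passes, the raw t-test is used. If it fails, the raw, log and square-root t-tests and the exact signed-rank test are all treated as available. Entries are lognormal / gamma at n=8 unless stated.

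| | Cmax | AUC |
|---|---|---|
| Check fails, on the differences | 9% / 7% | 13% / 9% |
| Check fails, on either dose's values | 27% / 18% | 42% / 35% |
| The two targets give opposite verdicts | about 29% / 22% | 38% / 33% |
| Analyses disagree on p<0.05, differences checked | 1.2% / 0.6% | 4.2% / 2.8% |
| Analyses disagree on p<0.05, either dose checked | 3.0% / 1.3% | 8.7% / 6.8% |
| Power, raw vs log, n=8 | 95 vs 98% / 96 vs 97% | 89 vs 96% / 89 vs 92% |
| Power, raw vs log, n=6 | 87 vs 90% / 87 vs 87% | 82 vs 86% / 78 vs 73% |

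At n=6 with either dose checked, disagreement is 5.2% / 3.4% (Cmax) and 9.3% / 8.0% (AUC). Over correlations 0.3 to 0.7 at n=8, either dose checked, it runs 0.4–4.7% (Cmax) and 3.7–10.4% (AUC).

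**Type I error.** With no dose effect, taking the most favourable of the four analyses once the check fails gives 4.7–5.6% false positives. Single analyses give 3.3–5.2%.

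**The case against.** The strongest reply is that this is an eight-person pilot and little turns on the gap. That largely stands. The purpose in section A.1 is to find the dose whose Cmax is closest to mouse levels, and that choice does not use this test. The AUC inputs are also imperfect: L.2 quotes AUC over 24 hours for asiatic acid alone, whereas the trial analyses AUC over 12 hours for many analytes. L.1 sets no hard 5% cut-off either; it combines density plots with a formal test, so the table is an illustration.

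A raw scale can be defended too. L.2's d values are raw-scale quantities, and a fixed raw scale would close the prespecification gap equally well. The case for logs is that the result is the ratio that L.2's proportionality assumption concerns, not a large gain in power.

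Three stronger readings are tempting and are not supported:

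- *tmax has no analysis at all.* L.1 derives it by non-compartmental analysis, promises descriptive summaries at each dose, and its rule for continuous variables covers tmax by default, with the rank option. What is missing is a method suited to it.
- *The differences are not checked.* L.1 does not say what the formal test is applied to, and the quantity it tests is the within-subject difference. Only silence can be asserted.
- *The false-positive rate or the sample size is compromised.* The figures above show neither for the pooled comparison.

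The word paired in front of rank-sum shows the intent, so that item is a correction of terms.

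**Conclusion.** The point holds as a prespecification and terminology gap, of minor severity. Certain from the text: no scale is fixed for Cmax or AUC, the fallbacks have no order, the paired rank test is misnamed, and tmax has no method of its own.

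Certain from L.2's own effect sizes: the within-gender statement is not delivered, with 57% and 49% power at n=4 by paired t-test and no possibility of significance by signed-rank.

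The effect on the pooled result is modest: disagreement on significance in about 1–4% of trials at n=8 if differences are checked and 1–9% if either dose's values are checked. Those ranges rest on asiatic acid data from 12 males (AUC over 24 hours), a correlation of 0.5, and lognormal or gamma shape.

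**What to change.** In L.1, replace the normality-check and fallback sentences with:

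> ln(Cmax) and ln(AUC0-12) are analysed by paired t-test as the primary dose comparison, without a normality pre-test, and reported as the 4 g/2 g geometric mean ratio with 95% CI. The covariate-adjusted regression on the same scale, the raw-scale t-test and the Wilcoxon signed-rank test are sensitivity analyses. Where a profile has no quantifiable value for an analyte, that result is summarised descriptively and left out of the log analysis. tmax is summarised by the median paired difference and range, with an exact signed-rank test that drops zero differences and reports their number.

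This also changes rank-sum to signed-rank and ranks the t-test above the regression. In L.2, delete the within-gender claim or restate it as descriptive, giving 57% and 49% power at n=4.

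The change is to wording only: no new data and no change in sample size. It has three costs.

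- If only six complete, log power for AUC could be somewhat lower than raw (73% against 78%, gamma) or higher (86% against 82%, lognormal).
- Leaving out unquantifiable profiles removes the lowest exposures, so their number should be reported. Section E's calibration ranges start at 25 ng/mL for asiatic acid and 5 ng/mL for madecassic acid and several caffeoylquinic acids and metabolites.
- Dropping zero tmax differences shrinks the signed-rank sample; with five or fewer non-zero pairs its p-value cannot go below 2/2⁵ = 0.0625.

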Gender differences have been observed in the incidence, development and progression of Alzheimer's disease, and in response to interventions targeting cognitive impairment. Women develop cognitive disability more rapidly compared to men.^{13,14} Previous studies of intranasal insulin for cognition showed functional abilities were better preserved in women compared to men.¹⁵ These differences highlight the importance of evaluating responses to any agent in both males and females. As part of this proposed project we will evaluate potential gender differences in bioavailability and pharmacokinetics.

C.2. *Centella asiatica*

Centella asiatica is a highly regarded botanical reputed in Eastern medicine to increase intelligence and memory.¹⁶ In Western countries, it is sold as the dietary supplement "gotu kola"¹⁷ for use in improving brain health and cognitive function. Preclinical studies have shown that *Centella asiatica* extracts have biological effects of relevance to memory, learning, aging, mood and potentially disease progression in Alzheimer's disease.¹⁸ Water extracts of *Centella asiatica* have improved learning and memory in wild-type rats,¹⁹ wild-type mice,^{20,21} and rats subjected to central nervous system toxicity.^{22,23} In addition, similar extracts have been shown to modify the brain structure by increasing hippocampal neuron dendritic arborization in adult rats,²⁴ neonatal rats,²⁵ and neonatal mice,²¹ potentially contributing to the observed cognitive changes. With regards to mood and behavior, ethanol extracts given to mice subjected to chronic and acute stress²⁶ and sleep deprivation²⁷ demonstrated anxiolytic properties. Similar ethanol extracts revealed antidepressant properties in rats.²⁸

Figure 1. *Centella asiatica* water extract improves learning and memory in aged female Tg2576 mice without altering β -amyloid accumulation. Tg2576 mice (20 month old) were exposed to *Centella asiatica* water extract (200mg/kg/day) in their drinking water for 2 weeks before and during testing (total 5 weeks). Left – Morris water maze escape times. Right – Soluble and insoluble fractions of A β were extracted from cortical tissue and analyzed via ELISA (bars represent means +/- standard error).

[figure not shown]
Study Title: A pharmacokinetic study of *Centella asiatica* in the elderly

Principal Investigator: [name]

IRB#: 17697

Date: Feb 28 2024

Protocol v4.0

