Power analysis and sample size estimation for the dose-dependent pharmacokinetics of *Centella asiatica* analytes were derived from the literature, specifically the plasma dose response analysis of the triterpene asiatic acid by Grimaldi et. al.⁴⁵ after single acute administration of 30 mg and 60 mg of a *Centella asiatica* triterpene fraction. In a repeated measures cohort of 12 males, they found significant differences ($p<0.05$) in asiatic acid's peak plasma concentration (C_{max}) (30 mg: $0.70 \mu\text{g/ml} \pm 0.38$; 60 mg: $1.36 \mu\text{g/ml} \pm 0.45$; $d=1.57$) and 24-hour total bioavailability (AUC_{0-24}) (30 mg: 4.16 ± 3.81 ; 60 mg: 9.39 ± 3.53 ; $d=1.42$) between the two doses. This paper was chosen as an analog for the current study since a proportionally equimolar dose response shift in the pharmacokinetic profile of asiatic acid can be expected of the proposed *Centella asiatica* product doses. Under that assumption, a significant within-group dose response at $\alpha=0.05$ with at least 80% power would be found for C_{max} with six participants and for AUC_{0-12} with seven participants. Even if the inclusion of additional compounds in the

Study Title: A pharmacokinetic study of *Centella asiatica* in the elderly

Principal Investigator: [name]

IRB#: 17697

Date: Feb 28 2024

Protocol v4.0

water extract reduces the dose effect anticipated in the current study, a significant difference in the pharmacokinetic outcomes would still be seen with eight participants. We therefore, propose a cohort of four men and four women, which will enable dose responses to be seen within each gender individually, and allow for evaluation of an attenuated response by pooling gender or provide protection against study dropout.

L.3. Data quality and management

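### Section L.2 says four men and four women will show dose responses within each gender, but the plan's own calculation needs six (Cmax) or seven (AUC); four give about 57% and 49% power

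*Combined protocol and SAP*

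**What the plan says.** Section L.2 takes its effect sizes from a published single-dose study of asiatic acid at 30 mg and 60 mg: "In a repeated measures cohort of 12 males, they found significant differences" between the two doses, with d=1.57 for Cmax and d=1.42 for AUC0-24. On that basis it says that "a significant within-group dose response at" alpha 0.05 with at least 80% power is obtained for Cmax "with six participants and for AUC_{0-12} with seven participants". It adds that, even if other compounds in the extract weaken the effect, "a significant difference in the pharmacokinetic outcomes would still be seen with eight participants". It concludes with four men and four women, "which will enable dose responses to be seen within each gender individually". Pooling the genders is kept for an attenuated response or as protection against dropout.

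Section C.1 gives the gender question its standing: "we will evaluate potential gender differences in bioavailability and pharmacokinetics". Section L.1 names paired t-tests with two-tailed significance at p<0.05. If normality fails it allows transformations or "non-parametric equivalent tests such as the paired Wilcoxon rank-sum test", and it says that "multiple comparison correction to p-values will be applied as necessary". Gender appears in L.1 only as a regression covariate. No separate effect size, correlation or power is given for one gender alone.

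**The concern.** The contradiction lies within one paragraph: six or seven people are needed to show a dose response, yet four are said to be enough in each gender.

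What is at stake is how the by-gender results will be read. L.2 is the only place that tells a reader what to expect from one gender, and it says that a dose response will be visible. Someone relying on it could take a significant result in one gender and a non-significant result in the other as evidence that the genders differ. With four per group, that pattern is likely by chance alone.

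**Working it through.** **Inputs.** From L.2: d=1.57 (Cmax), d=1.42 (AUC), alpha 0.05, target power 80%, four per gender; means ± SD for Cmax 0.70 ± 0.38 and 1.36 ± 0.45 µg/ml, and for AUC0-24 4.16 ± 3.81 and 9.39 ± 3.53. From L.1: paired t-test, two-sided.

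**Step 1: reproduce the plan's figures.** Power is the probability that a noncentral t variable with n−1 degrees of freedom and noncentrality d√n exceeds the two-sided 5% critical value (the opposite tail is negligible).

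| n | Critical t | d√n, Cmax | Power, Cmax | d√n, AUC | Power, AUC |
|---|---|---|---|---|---|
| 4 | 3.182 | 3.140 | 56.7% | 2.840 | 49.3% |
| 5 | 2.776 | 3.511 | 74.7% | 3.175 | 66.6% |
| 6 | 2.571 | 3.846 | 86.3% | 3.478 | 79.2% |
| 7 | 2.447 | 4.154 | 93.0% | 3.757 | 87.6% |
| 8 | 2.365 | 4.441 | 96.6% | 4.016 | 92.9% |

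The first n to reach 80% is six for Cmax and seven for AUC, exactly as L.2 states. A one-sided t-test would give five and five, and a two-sided normal approximation four and four, so neither is the plan's method.

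**Step 2: apply the same calculation to one gender.** The n=4 row gives 56.7% and 49.3%. Simulation with 1,000,000 replicates gives 56.8% and 49.3%. One dropout within a gender (n=3) leaves 33.8% and 29.3%.

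**Step 3: what four would need.** 80% power at n=4 requires d of about 2.13. With within-person correlation r, d = (m2−m1)/√(s1²+s2²−2·r·s1·s2). The stated d values imply r of about 0.50 for both measures. Reaching 2.13 needs r of about 0.73 (Cmax) or 0.78 (AUC). The documents do not give r. Over an assumed range, n=4 gives 45% and 38% at r=0.3, and 76% and 69% at r=0.7.

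**Step 4: comparing two p-values.** Take independent groups with the same true effect and power p in each:
- both significant, p²: 0.567² = 32% (Cmax); 0.493² = 24% (AUC)
- exactly one significant, 2p(1−p): 49%; 50%
- neither, (1−p)²: 19%; 26%

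**Step 5: precision at r=0.5.** The SD of the within-person difference is √(0.38²+0.45²−0.38×0.45) = 0.419 for Cmax and √(3.81²+3.53²−3.81×3.53) = 3.678 for AUC.
- 95% CI half-width in one gender, 3.182×SD/√4: 0.67 against an expected difference of 1.36−0.70 = 0.66; and 5.85 against 9.39−4.16 = 5.23.
- Half-width for men minus women (6 df), 2.447×SD×√(2/4): 0.73 and 6.36, larger than the whole expected dose effect.

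**Step 6: non-parametric fallback.** The smallest exact two-sided p of the paired Wilcoxon (signed-rank) test is 2/2ⁿ. For n=4 it is 2/16 = 0.125, so p<0.05 is impossible. For n=8 it is 0.008.

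**Step 7: the attenuation sentence.** Eight completers keep 80% power down to d of about 1.16. That is a loss of 1−1.156/1.57 = 26% for Cmax or 1−1.156/1.42 = 19% for AUC. L.2 states no such limit.

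**The case against.** The strongest reply is that the gender clause states no power, alpha or test. It could mean only that responses will be observed by gender, in a pilot whose endpoints and aims do not mention gender. This reading does not survive the context. The sentence just before uses the same verb for a significant difference, the clause is drawn as a conclusion from a power statement, and pooling is reserved for a weaker effect or for dropout. Four per gender is therefore presented as enough for the full expected effect.

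Several narrower objections do stand:
- L.1 lists no within-gender test and no comparison of two p-values, so Step 4 shows a risk of misreading, not a planned analysis.
- C.1 promises an evaluation of gender differences. That is a different contrast from a dose response within each gender, and it carries no promise of significance.
- The Wilcoxon limit applies only if normality fails, transformation is not used, and the test is run within one gender.
- The d values come from 12 men and from AUC0-24, so applying them to women and to AUC0-12 is extrapolation.
- The pooled figures need their own limits. They rest on asiatic acid Cmax and AUC and say nothing about tmax or the caffeoylquinic acids. At the six completers that section F.2.1 describes as still powered, AUC power is 79.2%. If a Bonferroni correction over the three primary parameters is assumed, eight completers give 86% (Cmax) and 78% (AUC).

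None of these makes four sufficient.

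**Conclusion.** The concern holds and should be fixed. By the plan's own method, four participants give about 57% power for Cmax and 49% for AUC, against a stated target of at least 80%. These figures are conditional on the source study's effect sizes, unadjusted two-sided alpha 0.05 and no dropout; dropout or a multiplicity correction would lower them. Four reach 80% only if within-person correlation is well above the value of about 0.5 that the plan's effect sizes imply. The comparison of four with six and seven needs none of these extra assumptions. The fault is confined to the within-gender statement and, as a lesser point, the unbounded attenuation sentence. The choice of eight participants for the pooled comparison is not in question.

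**What to change.** In L.2:
- Delete the clause saying that dose responses will be seen within each gender.
- State that only the pooled dose comparison is powered: eight completers give about 97% for Cmax and 93% for AUC. Make this conditional on the asiatic acid effect sizes from 12 men and on unadjusted two-sided alpha 0.05, and say that power is lower with dropout or a multiplicity correction.
- State that the by-gender evaluation promised in C.1 is descriptive at four per gender. It would report the dose effect in men, in women, and the difference between them, each with a 95% confidence interval, and would not compare two p-values.
- Limit the attenuation sentence to say that eight completers keep 80% power for d of about 1.16 or more.

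In L.1, repeat the sentence on descriptive by-gender reporting.

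The cost is a few sentences and a small descriptive analysis, with no extra participants, visits or samples. The one downside is that the plan's claim for by-gender results becomes less favourable.
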